7.6.4 Sensitivity Analysis

Analyses of the primary efficacy endpoint (improvement in liver fibrosis and no worsening of steatohepatitis at Week 24) in the PPS and FAS will be performed as a sensitivity analysis. Analyses of secondary endpoints of resolution of steatohepatitis and no worsening of liver fibrosis at Week 24 and improvement in liver fibrosis at Week 24 will also be presented for the PPS and FAS.

In addition, tipping point analysis will be performed to evaluate various deviations from the assumption of non-response for the primary efficacy endpoint in the FAS. For subjects with missing liver biopsy data at Week 24, responder status will be imputed in an increasing manner by subject level for each treatment group. Specifically, for each subject, a responder/non-responder status will be imputed with the scenario where all subjects being non-responders up to the scenario where all subjects are responders. This will include all possible scenarios of responder status for all missing data, including scenarios where subjects on EFX groups have worse outcomes than subjects on placebo (see table below). For each scenario, an analysis similar to the primary analysis will be performed.

"Response" in Missing in Placebo Group	"Response" in Missing in EFX Group						
	0	1	2	...	m-2	m-1	m [1]
0	p=0.xxx	p=0.xxx	p=0.xxx	p=0.xxx	p=0.xxx	p=0.xxx	p=0.xxx
1	p=0.xxx	p=0.xxx	p=0.xxx	p=0.xxx	p=0.xxx	p=0.xxx	p=0.xxx
2	p=0.xxx	p=0.xxx	p=0.xxx	p=0.xxx	p=0.xxx	p=0.xxx	p=0.xxx
...	p=0.xxx	p=0.xxx	p=0.xxx	p=0.xxx	p=0.xxx	p=0.xxx	p=0.xxx
n-2	p=0.xxx	p=0.xxx	p=0.xxx	p=0.xxx	p=0.xxx	p=0.xxx	p=0.xxx
n-1	p=0.xxx	p=0.xxx	p=0.xxx	p=0.xxx	p=0.xxx	p=0.xxx	p=0.xxx
n [2]	p=0.xxx	p=0.xxx	p=0.xxx	p=0.xxx	p=0.xxx	p=0.xxx	p=0.xxx

[1] m = total number of subjects with missing data at Week 24 in EFX group

[2] n = total number of subjects with missing data at Week 24 in Placebo group

7.6.5 Subgroup Analysis

Subgroup analysis will be performed for the efficacy endpoints (see [Table 4](#)). The group variables are as follows:

Statistical Analysis Plan

Sponsor Name: Akero Therapeutics, Inc.
Sponsor Protocol ID: AK-US-001-0102

- Baseline T2D (yes or no)
- Baseline fibrosis score (F2 or F3)
- Statin use at baseline (yes or no)
- Endogenous FGF21 at baseline (>median or ≤median)
- Pro-C3 at baseline (<14 µg/mL or ≥14 µg/mL)
- Baseline hypertension status (yes or no)
- BMI categories at Baseline (>median or ≤median)

Additional subgroups will be presented for the primary efficacy endpoint as follows:

- Age categories (<65 years, ≥65 years, ≥75 years)
- Ethnicity (Hispanic or Latino, not Hispanic or Latino)
- NAS at Screening (≤5, >5)
- Baseline liver fat (<10%, ≥10% to <20%, ≥20%)

Table 4 Summary of Subgroup Analysis

Endpoint	Subgroup
Primary: improvement in liver fibrosis (one stage) and no worsening of steatohepatitis at Week 24	LBAS subgroups: age category, ethnicity, NAS at Screening, baseline liver fat, baseline T2D, baseline fibrosis score, statin use at baseline, endogenous FGF21 at baseline, and baseline BMI category
Secondary: resolution of steatohepatitis and no worsening of liver fibrosis at Week 24 and 96	LBAS subgroups: baseline T2D, baseline fibrosis score, and statin use at baseline
Secondary: improvement in liver fibrosis (≥ one stage) at Week 24 and 96	LBAS subgroups: baseline T2D, baseline fibrosis score, and statin use at baseline
Secondary: change from baseline in hepatic fat fraction by MRI-PDFF at Week 24 and 96	MRI-PDFF Analysis Set subgroups: baseline T2D, baseline fibrosis score, statin use at baseline, and baseline liver fat
Secondary: improvement in liver fibrosis (one stage) and no worsening of steatohepatitis at Week 96	LBAS subgroups: age category, ethnicity, NAS at Screening, baseline liver fat, baseline T2D, baseline fibrosis score, statin use at baseline, endogenous FGF21 at baseline, and baseline BMI category
Secondary: lipoproteins (Lp (a), total cholesterol, triglycerides, Non-HDL-C, HDL-C, LDL-C and LDL-P) and markers of	FAS subgroups: statin use at baseline, baseline T2D, and baseline fibrosis score

CONFIDENTIAL

Statistical Analysis Plan

Sponsor Name: Akero Therapeutics, Inc.
Sponsor Protocol ID: AK-US-001-0102

Fortrea Study ID: 000000208791

Endpoint	Subgroup
lipid metabolism (ApoB and ApoC-III) change from baseline	
Secondary: markers of glycemic control (HbA1c, C-peptide, Adiponectin and HOMA-IR) change from baseline	Biomarkers Analysis Set subgroups: baseline T2D and statin use at baseline
Secondary: serum fibrosis biomarkers (ELF, Pro-C3, C3M, NIS-4) change from baseline	Biomarkers Analysis Set subgroups: baseline T2D, baseline fibrosis score, and statin use at baseline for ELF, Pro-C3, C3M, and NIS-4; Pro-C3 at baseline for Pro-C3
Secondary: liver stiffness change from baseline	LBAS subgroups: baseline T2D, baseline fibrosis score, and statin use at baseline
Secondary: body weight change from baseline	FAS subgroups: baseline BMI category, baseline T2D, baseline fibrosis score
Exploratory: improvement in liver fibrosis (one stage) and resolution of steatohepatitis at Week 96	LBAS subgroups: age category, ethnicity, NAS at Screening, baseline liver fat, baseline T2D, baseline fibrosis score, statin use at baseline, endogenous FGF21 at baseline, and baseline BMI category
Exploratory: fibrosis stage and NAFLD Activity Score (NAS) on liver histology at Week 24	LBAS subgroups: baseline T2D and baseline fibrosis score
Exploratory: improvement in liver fibrosis (\geq two stages) and no worsening of steatohepatitis at Week 24 and two stage improvement in liver fibrosis at Week 24	LBAS subgroups: baseline T2D, baseline fibrosis score, and statin use at baseline
Exploratory: cardiovascular and metabolic risk factors (blood pressure)	Safety Set subgroup: baseline hypertension status
Exploratory: MRI-PDFF based quantitation of hepatic fat	MRI-PDFF Analysis Set subgroups: baseline T2D, baseline liver fat
Exploratory: health-related quality of life (CLDQ-NASH) change from baseline	FAS subgroups: baseline T2D

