observed across all EFX groups in HDL-C (increases ranging from 14.03 to 15.80 mg/dL), non HDL-C (decreases ranging from 23.33 to 31.47 mg/dL), and triglycerides (decreases ranging from 71.03 to 89.62 mg/dL). Most importantly, there were no increases in LDL-C across EFX groups. Additionally, a significant LDL-C reduction was noted in the 28 mg EFX group compared to placebo.

Clinically meaningful improvements in glycemic control and weight loss were reported at all doses, including the first report of significant weight loss in 1 cohort. Significant reductions at Week 16 were observed in HbA1c for the 50 and 70 mg dose groups (-0.39% and -0.50%, respectively). Clinically meaningful improvements were also observed for insulin resistance as measured by HOMA-IR, adiponectin, and C-peptide. For HOMA-IR, significant reductions in the 50 and 70 mg EFX groups were reported (7.675 and 8.775, respectively), while adiponectin levels increased significantly in a dose-related fashion by 2.8486 to 5.6437 mg/dL across all EFX groups. As expected with the improved insulin sensitivity and glycemic control, C peptide levels were significantly lower in all EFX groups (1.724 to 2.063 µg/L). Lastly, mean weight decreases were reported in all EFX groups, with a statistically significant reduction of 2.80 kg (placebo-adjusted 3.27 kg), in the 70 mg dose group.

Two serum biomarkers of liver fibrosis were measured: the diagnostic marker ELF Score, which is comprised of HA, TIMP-1 and amino terminal Pro-C3; and Pro-C3, a marker of new collagen synthesis or fibrogenesis.

There was a significant reduction from baseline to Week 12/LOCF in LS mean ELF Score of -0.702 (p<0.0001), -0.745 (p<0.0001), -0.435 (p=0.0089) in the 28, 50, and 70 mg EFX groups, respectively. When compared to placebo, the change from baseline in ELF Score at Week 12/LOCF was statistically significant for all 3 EFX groups (p≤0.0341).

Pro-C3 levels decreased from baseline after 16 weeks of treatment with EFX, indicating reduced rates of synthesis of collagen in the liver of NASH subjects. Significant reductions from baseline to Week 16/LOCF in LS mean Pro-C3 values of -6.04 (p<0.0001), -4.72 (p<0.0001), and -5.94 µg/L (p<0.0001) were observed in the 28, 50, and 70 mg EFX groups, respectively. When compared to placebo, the change from baseline in Pro-C3 at Week 16/LOCF was statistically significant for all 3 EFX groups (p≤0.0038).

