7.4 Demographics and Other Baseline Characteristics

Demographic and baseline measurements will be listed and summarized by treatment group and in all EFX subjects and total for All Randomized Subjects.

The following demographic and baseline characteristics will be summarized:

- Age (years)
- Age categories (<65 years, ≥65 years, ≥75 years)

CONFIDENTIAL

Statistical Analysis Plan

Sponsor Name: Akero Therapeutics, Inc.
Sponsor Protocol ID: AK-US-001-0102

- Sex
- Race
- Ethnicity
- Height (cm) at Screening
- Weight (kg) at Baseline
- Body mass index (BMI) (kg/m²) at Baseline
- BMI categories at Baseline (<30 kg/m², ≥30 kg/m²)
- Waist circumference (cm) at Baseline
- Hip circumference (cm) at Baseline
- Waist-to-hip ratio at Baseline
- T2D status at Screening
- Fibrosis stage at Screening
- Statin use at baseline
- Vitamin E/ Thiazolidinedione use at baseline
- NAS and NAS components at Screening
- Median Liver Stiffness Measurement (LSM) in kiloPascals (kPa) as Evaluated by FibroScan at Screening
- Median Controlled Attenuation Parameter (CAP) at Screening
- ALT (U/L) and AST (U/L) at Baseline
- ALT and AST categories at Baseline (≤ULN, >ULN)
- Systolic blood pressure at baseline, Diastolic blood pressure at baseline, and Systolic blood pressure category at baseline (<130mmHg, ≥130mmHg)
- Fasting values of Triglyceride (mg/dL), Total Cholesterol (mg/dL), LDL-C (mg/dL), HDL-C (mg/dL), and non-HDL-C (mg/dL) at Baseline
- Endogenous FGF21 at Baseline
- Serum fibrosis biomarkers: ELF score, Pro-C3 (μg/mL), C3M, Pro-C3/C3M, NIS-4 at Baseline
- Pro-C3 categories at Baseline (<14 μg/mL, ≥14 μg/mL)
- Liver Injury Biomarkers: MELD score and CP score at Baseline
- Bone Biomarkers: P1NP and CTX-1 at Baseline

CONFIDENTIAL

Document Date: 07 Feb 2024

Page 30 of 60
ST-AD-008 version 05

Statistical Analysis Plan

Sponsor Name: Akero Therapeutics, Inc.
Sponsor Protocol ID: AK-US-001-0102

- Insulin Sensitivity and Glycemic Control Biomarkers: Hemoglobin A1c (%), Fasting values of Insulin, Blood Glucose, Adiponectin, and HOMA-IR at Baseline

Other baseline measurements, such as safety laboratory, ADA, vital signs, and ECG, will be summarized by treatment group with the post-baseline measurements.

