All laboratory data will be reported in Conventional units. Out-of-reference-range values will be flagged as high (H) or low (L) in the listings. For analysis purposes, values preceded by a "<" or a ">" sign (i.e. those below or above the limits of quantification) will be considered equal to the lower or upper limit of quantification, respectively.

Baseline for each laboratory analyte is the pre-dose measurement on Baseline visit (Day 1) with exceptions as defined in Section 7.1.1. For post-baseline, within an analysis visit window, the analyte measurement from the scheduled visit will be used if available. If multiple scheduled visits occur within a single visit window, then the visit closest to the target day of the visit window will be used in the analysis. If there is a tie, the later visit will be used in the analysis.

Statistical Analysis Plan

Sponsor Name: Akero Therapeutics, Inc.
Sponsor Protocol ID: AK-US-001-0102

If no scheduled visit occurs, the measurement from the unscheduled visit closest to the defined target analysis day within the window will be used. If there is more than one measurement with equal distance to the defined target analysis day, the latter will be used. If no visits occur within a visit window, the measurement for this visit will be treated as missing.

Laboratory values will be assigned toxicity grades, when available, using criteria based on the NCI-CTCAE, version 5.0 (Table 6). These criteria are derived using only the numeric laboratory measurement, baseline measurement and normal range limits. Where defined, low and high shifts will be summarized separately. The incidence of treatment-emergent laboratory abnormalities, defined as values that increase at least one toxicity grade from baseline at any scheduled or unscheduled post-baseline assessment up to and including the date of last dose of study drugs plus 30 days, will be summarized by treatment group and visit. If baseline data are missing, then any graded abnormality (i.e., at least a Grade 1) will be considered treatment-emergent. The percentage incidence of graded treatment-emergent abnormalities will be calculated out of the number of subjects with non-missing value at the specified time point.

Table 6 Laboratory Toxicity Grade Criteria of Selected Clinical Laboratory Assessments

Serum Chemistry	CTCAE Term	Grade 1	Grade 2	Grade 3	Grade 4

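### Pro-C3 is in µg/mL in the SAP and µg/L in the protocol: reconcile the 1,000-fold gap, because the 14 µg/mL cut-off applied literally would very probably leave its upper category empty

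*SAP*

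**What the plan says.** The SAP states a unit for Pro-C3 in three places, and it is µg/mL each time.

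- SAP 7.4, baseline summary: "Serum fibrosis biomarkers: ELF score, Pro-C3 (μg/mL".
- SAP 7.4, baseline categories: "Pro-C3 categories at Baseline (<14 μg/mL, ≥14 μg/mL".
- SAP 7.6.5, subgroup variables: "Pro-C3 at baseline (<14 µg/mL or ≥14 µg/mL".

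Table 4 in SAP 7.6.5 uses the subgroup variable once, within the row for change from baseline in serum fibrosis biomarkers: "Pro-C3 at baseline for Pro-C3". Change from baseline in Pro-C3 is a secondary endpoint in SAP 3.2.

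The protocol gives Pro-C3 results once, in section 1.4.1.3 on the Phase 2a study: "Significant reductions from baseline to Week 16/LOCF in LS mean Pro-C3 values of -6.04 (p<0.0001), -4.72 (p<0.0001), and -5.94 µg/L (p<0.0001", for 28, 50 and 70 mg respectively. The unit there is µg/L.

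SAP 7.7.3 has a general rule on laboratory units, "All laboratory data will be reported in Conventional units", but does not say what that means for Pro-C3. Protocol Table 5 lists Pro-C3 among the fibrosis biomarkers without a unit. Neither document gives a conversion, a baseline Pro-C3 level, or a source for the figure 14.

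**The concern.** A cut-off is an operative instruction: it decides which subjects fall in which row. The SAP's cut-off is stated in a unit 1,000 times larger than the unit in the sponsor's own earlier results for the same marker. If the protocol's scale is the true one, a threshold of 14 µg/mL lies far above any level consistent with those results. The baseline category would then put everyone in one row, and the prespecified subgroup analysis could not be run.

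The alternative is that someone applies the number 14 without its unit. The split may then work, but only because the specification was not followed, and the outputs would carry a unit that is wrong by a factor of 1,000.

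**Working it through.** **Inputs**

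- Cut-off: 14 µg/mL (SAP 7.4 and 7.6.5).
- Phase 2a LS mean changes in Pro-C3 at Week 16/LOCF: -6.04, -4.72 and -5.94 µg/L for 28, 50 and 70 mg, each p<0.0001 against baseline (protocol 1.4.1.3).
- Group sizes: 19, 20 and 20 (protocol Table 1, full analysis set). The number contributing to the Pro-C3 analysis is not given, so these sizes are approximate for this purpose.
- Baseline Pro-C3: not given, so a range is assumed below.

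The SAP shows no derivation of the cut-off, so there is no planned figure to reproduce.

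**Step 1: put the cut-off on the protocol's scale.** 14 µg/mL × 1,000 mL/L = 14,000 µg/L.

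**Step 2: compare with the reported changes.** A cut-off is a level and the protocol gives changes, so this shows scale only.

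| Dose | Change (µg/L) | 14,000 ÷ change | Change as % of 14,000 |
|---|---|---|---|
| 28 mg | 6.04 | 2,318 | 0.043% |
| 50 mg | 4.72 | 2,966 | 0.034% |
| 70 mg | 5.94 | 2,357 | 0.042% |

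**Step 3: from change to level, by an assumed relative reduction.** Mean baseline = change ÷ relative reduction.

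- Upper end, a 10% reduction and the largest change: 6.04 ÷ 0.10 = 60.4 µg/L.
- Lower end, an 80% reduction and the smallest change: 4.72 ÷ 0.80 = 5.9 µg/L.

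The mean baseline is then about 6 to 60 µg/L. As a share of the cut-off this is 5.9 ÷ 14,000 = 0.04% to 60.4 ÷ 14,000 = 0.43%. Even at the upper end, a subject would need a value 14,000 ÷ 60.4 ≈ 232 times the mean to reach the higher category.

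**Step 4: a second route, from the p-values.** With p<0.0001 two-sided (normal quantile 3.89), the standard error is at most change ÷ 3.89, and the SD of change is at most that times √n.

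- 28 mg: 6.04 ÷ 3.89 = 1.55; × √19 gives about 6.8 µg/L.
- 50 mg: 4.72 ÷ 3.89 = 1.21; × √20 gives about 5.4 µg/L.
- 70 mg: 5.94 ÷ 3.89 = 1.53; × √20 gives about 6.8 µg/L.

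These bounds are approximate, because the estimates are model-based LS means with LOCF. If within-subject error is independent at the two visits, SD of change is at least √2 × CV × baseline, so baseline is at most SD ÷ (√2 × CV). A mean baseline of 14,000 µg/L would need a within-subject CV of about 6.8 ÷ (1.414 × 14,000) = 0.03%. For assumed CVs of 1%, 5%, 10% and 15%, the largest mean baseline across the three doses is about 480, 97, 48 and 32 µg/L.

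**Step 5: the same figure in the protocol's unit.** 14 µg/L (= 14 ng/mL = 0.014 µg/mL) lies inside the 6 to 60 µg/L range of Step 3, so both categories could be populated. This shows compatibility. It does not show that 14 µg/L was intended.

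**The case against.** The unit conflict itself is hard to dispute: the SAP's unit is the same in all three places, so it is not an extraction fault. The case on the other side concerns what follows from it.

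**Emptiness is inferred.** The documents report mean changes and no baseline level. A reader might conclude that the upper group is certainly empty and the contrast wholly lost. The documents do not support that as fact. It needs the assumptions in Steps 3 and 4, and it holds only if the protocol's unit is the right one and the cut-off is applied with its unit. This objection stands, and the conclusion is worded accordingly. It does not remove the point, because both routes leave the written cut-off far out of range.

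**The right unit is not established.** A reader might also infer that 14 makes sense only in µg/L. Neither document says where 14 comes from. If the protocol's unit were the wrong one and its values were really in µg/mL, the same arithmetic would give a mean baseline of about 6 to 60 µg/mL and the SAP split would work. This too stands, so the laboratory's unit must be checked before any text is changed.

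**A programmer will simply use 14.** Perhaps so, and if the data are held in µg/L the grouping would be usable. The label would still be wrong by a factor of 1,000, and correct execution would depend on disregarding the specification.

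**The reach is small.** This stands. The variable is not assigned to the primary or any histological endpoint, and the main Pro-C3 MMRM in SAP 7.6.2.7 does not use the cut-off. Nor do the documents say that subjects with high baseline Pro-C3 are the more informative group, so the point should not be given extra weight on that ground.

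**Conclusion.** The point holds as a unit conflict with a conditional consequence. SAP 7.4 and 7.6.5 and protocol 1.4.1.3 state Pro-C3 in units that differ by exactly 1,000, and nothing in either document resolves it.

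What follows depends on two things the documents do not settle: which unit is right, and whether the threshold is applied with its unit.

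- Protocol unit right, cut-off applied literally: the upper baseline category and subgroup are very probably empty. This rests on an assumed relative reduction of 10% to 80%, with the p-value bound as support.
- Protocol unit right, bare 14 applied to data in µg/L: the split works and the outputs are mislabelled 1,000-fold.
- SAP unit right: the split works and the protocol's background figures carry the error.

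The effect is confined to the baseline Pro-C3 summary, the baseline Pro-C3 category, and the baseline Pro-C3 subgroup for change from baseline in Pro-C3. The primary analysis, its type I error and the main Pro-C3 model are unaffected. It is still worth correcting, because it is an operative threshold for a prespecified subgroup of a secondary endpoint.

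**What to change.** 1. Confirm the Pro-C3 reporting unit in the central laboratory's data transfer specification, and check the figure 14 against that unit.
2. Then correct the unit in the three SAP places (two bullets in 7.4, one in 7.6.5) and in the matching table shells. If the protocol's unit is confirmed, this becomes µg/L (= ng/mL). If the SAP's unit is confirmed, correct the protocol's background figures instead.
3. Do this before programming. If any Pro-C3 subgroup or baseline category output already exists, check whether the cut-off was applied with its unit or as a bare number, and relabel or rerun it as needed.

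The cost is one check with the laboratory, three unit corrections and the shell updates. No analysis method changes.

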7.7 Safety

All safety data collected on or after the date that study drug is first dispensed up to the date of last dose of study drugs plus 30 days will be summarized by treatment group and total (as applicable). Data for the follow-up period will be included in data listings.

7.7.1 Extent of Exposure

Weeks of exposure to study drug will be calculated as:

Statistical Analysis Plan

Sponsor Name: Akero Therapeutics, Inc.
Sponsor Protocol ID: AK-US-001-0102

(date of last dose of study drug - date of first dose of study drug + 7) / 7

Weeks of exposure to study drug will be summarized by treatment based on the Safety Set with descriptive statistics and with counts and percentages of subjects with exposure in the following categories:

- >0 to \leq 4 weeks
- >4 to \leq 8 weeks
- >8 to \leq 12 weeks
- >12 to \leq 16 weeks
- >16 to \leq 20 weeks
- >20 to \leq 24 weeks
- >24 to \leq 52 weeks
- >52 weeks to \leq 72 weeks
- >72 weeks

The total number of injections administered will be calculated for each subject. A contingency table will be provided to display the number and percentage of subjects in each treatment group with the following number of injections: 1-10, 11-20, 21-30, 31-40, 41-50, 51-60, 61-70, 71-80, 81-90, and >90.

7.7.2 Adverse Events

Clinical and laboratory AEs will be coded using the MedDRA Version 23.1 (or a later version if updated during the study). SOC, High-Level Group Term (HLGT), High-Level Term (HLT), PT, and Lower-Level Term (LLT) will be attached to the clinical database. AE severity will be graded using the National Cancer Institute-Common Terminology Criteria for Adverse Events (NCI-CTCAE, version 5.0). The relationship between an AE and study drug will be assessed (Related/ Not related) and also the relationship to study procedures.

AEs will be classified as either pre-treatment AEs or TEAEs as follows:

- pre-treatment AEs are events that start prior to the date of first dose of study drug.
- TEAEs are events with start date on or after the date of first dose of study drug and up to 30 days after date of last dose of study drug.

Any AEs leading to premature discontinuation of study drug will be summarized separately.

CONFIDENTIAL

Document Date: 07 Feb 2024

Page 44 of 60
ST-AD-008 version 05

Statistical Analysis Plan

Sponsor Name: Akero Therapeutics, Inc.
Sponsor Protocol ID: AK-US-001-0102

An overview table will summarize the number and percentage of subjects with at least one of the following AEs, where subjects with more than one event in a particular category are counted only once in that category:

- Any TEAEs;
- Any TEAEs by maximum severity grade (a subject will be counted in only one category);
- Study drug-related TEAEs (overall and by maximum severity);
- Study procedure related TEAEs (overall and by maximum severity);
- Any TEAEs of special interest (overall, injection site reaction, diarrhea, hypoglycemia, neurological or psychiatric event, or DILI)
- Any TEAEs of decompensated liver disease events including ascites, hepatic encephalopathy (HE), or variceal bleeding;
- Any SAEs;
- Any treatment-emergent SAEs (TESAEs);
- Any TEAEs leading to premature discontinuation of study drug;
- Any TEAEs leading to premature discontinuation of study from the end of study eCRF;
- Any TEAE leading to death.

Summaries (number and percentage of subjects) will be presented by SOC and PT for each of the categories in the overview (with the exception of Any TEAEs leading to premature discontinuation of study). Common TEAEs (PTs with an incidence $\geq 15\%$ in any treatment group) will be presented by SOC and PT as well.

Summaries will also be presented by SOC, PT and maximum severity grade for TEAEs, study drug-related TEAEs, and study procedure related TEAEs. In these summaries, subjects with more than one AE within a particular SOC are counted only once for that SOC. Similarly, subjects with more than one AE within a particular PT are counted only once for that PT. For summaries by maximum severity grade, subjects with multiple AEs within a particular SOC or PT will be counted under the category of their most severe AE within that SOC or PT.

All AEs collected during the course of the study will be presented in data listings with fields for treatment-emergent event (Yes / No), Start and end dates, Outcome (Fatal / Not resolved or Not recovered / Recovered or resolved / Recovered or resolved with sequelae [describe sequelae] / Unknown), Relationship to study treatment (Related / Not related), Relationship to study procedures (Related [specify procedure] / Not related), Toxicity Grade (CTCAE v 5.0), Action taken with the study drug (Dose not changed/ Drug interrupted/ Drug withdrawn/ Not

Statistical Analysis Plan

Sponsor Name: Akero Therapeutics, Inc.
Sponsor Protocol ID: AK-US-001-0102

applicable), Any other action (Yes [specify]/ No), Event of clinical interest (DILI/ Injection site reaction/ Diarrhea/ Hypoglycemia/ Neurological or Psychiatric event).

In addition, corresponding listings of SAEs and additional SAE details, AESIs and separate listing details of DILI and injection site reactions, decompensated liver disease events, TEAEs leading to discontinuation of study drug, and AEs leading to death will be produced.

